## **6.2. Summary of Nonclinical and Clinical Studies**

### **6.2.1. Nonclinical Studies**

EXN407 has undergone an extensive nonclinical safety evaluation. All nonclinical studies conducted for EXN407 are described in detail in the EXN407 IB.

*In vitro* pharmacology studies were performed to determine inhibitory dose response effect of EXN407 on SRPK1, to assess the selectivity of EXN407, and to assess the inhibitory dose response effect of EXN407 on kinases closely related to SRPK1. Functional studies were also conducted.

*In vivo*, EXN407 was extensively evaluated in mouse, rat and NHP models for toxicity, ocular tolerance, and pharmacokinetics. Plasma binding was assessed in plasma from the mouse, rat, rabbit, dog, cynomolgus monkey and human.

The results demonstrate EXN407 concentrations in ocular tissues follow a dose dependent relationship and are above levels required for efficacy in RPE cells, consistent with pharmacodynamic readouts at these concentrations on SRPK1 inhibition and pro-angiogenic VEGF-Axxxx reduction. EXN407 has sufficient posterior ocular permeability to distribute to the RPE/choroid for efficacy, combined with much lower systemic exposure, which would limit potential for any effects outside the eye.

### **6.2.2. Clinical Studies**

This is a FIH Phase Ib/II study of EXN407.

### 6.3. Summary of Potential Risks and Benefits

EXN407 is an investigational drug and the safety profile in humans has not yet been established because it has not been administered to any human subjects. It is therefore recommended that subjects are carefully monitored during administration of EXN407 until sufficient human experience is obtained to determine its safety.

Hypersensitivity reactions may occur in susceptible individuals.

No adverse reactions have been noted after *in vivo* good laboratory practice (GLP) repeat dose ocular toxicity studies in the rat and monkeys administered repeat doses of up to 0.015 mg/eye/dose (1.5 mg/mL, total dose of 0.06 mg/eye/day) and up to 0.0525 mg/eye/dose (1.5 mg/mL, total dose of 0.21 mg/eye/day), respectively (total four doses per eye per day) for 13 weeks. Total human dose in this study will be up to 0.09 mg/day (1.5 mg/mL).

As systemic absorption is anticipated to be very low based upon nonclinical data, the possibilities of direct drug related systemic adverse effects are also anticipated to be very low.

One potential benefit to subjects with a visual acuity better than an approximate Snellen equivalent of 20/32 (6/9, 78 letters) or worse than 20/160 (6/48, 39 letters) who are not offered intravitreal anti-VEGF injections, due to the lack of reimbursement from the public healthcare system for example in Australia, or who decline injection, but who do experience clear center involved DME is that they could potentially benefit from treatment that manages the VEGF165b/VEGF165a ratio in the eye.

EXN407 has the potential to be a non-invasive alternative to intravitreal anti-VEGF injections. Subjects with DME who may be unsuitable for or put off by the need for an intravitreal injection may benefit from EXN407 eye drops. It is important to note that subjects who participated in the landmark studies with anti-VEGFs had had DME on average for 1.6 - 2.4 years ([Nguyen 2012](#)). Despite this, approximately 30% of those randomized to receive sham treatment did not need any rescue treatment during the first 6 months of follow-up. Since participants in this study will be identified early, the slight delay caused by the study is not expected to be a significant risk for disease progression. To ensure subject safety, all subjects will be closely monitored and, if any subject shows a clinically significant deterioration in CMT and/or BCVA, they will be withdrawn in a timely manner and offered the standard of care.

### 6.4. Dosage and Treatment Periods

Up to three dose levels of EXN407 (with vehicle-control) are planned across three or more sequential cohorts. No intra-subject dose escalation or decrease will occur.

The dose levels to be explored are described in [Table 4](#). Decisions to escalate or expand the dose will be dependent upon review of emerging safety data by a DEC. The Sponsor will chair the DEC, which will be comprised of a Sponsor-led group. The DEC will conduct a review of safety data from each preceding cohort prior to commencing dosing in each proceeding cohort. Details will be provided in a DEC charter document.

**Table 4: EXN407 Dose Levels**

EXN407	Dose Expansion
Low-Dose 0.5 mg/mL (0.05%) EXN407 OR placebo (vehicle, i.e., excipient only)	The highest well-tolerated EXN407 dose (as determined by the DEC, study MM [REDACTED] and Sponsor MM), treatment with EXN407 or vehicle for up to 3 months
Mid-Dose 1.0 mg/mL (0.1%) EXN407 OR placebo (vehicle, i.e., excipient only)	
High-Dose 1.5 mg/mL (0.15%) EXN407 OR placebo (vehicle, i.e., excipient only)	

Both EXN407 and placebo (vehicle) are to be administered as one drop BID

#### **6.4.1. Initial Dosing Initiation and Continuation**

##### *Cohort 1 Sentinel Subjects (low-dose)*

The first two subjects in cohort 1 will be sentinel subjects (1 subject each randomized to EXN407 and vehicle) and will be dosed at least 1 week prior to the other three subjects of the cohort.

Immediately after dosing, and 48 hours and 72 hours post dosing (days 3 and 4) subjects in cohort 1 will be examined clinically for signs of intolerance of the study drug. If in the opinion of the Investigator the study drug has acceptable tolerability the subject will continue to be dosed through Day 7. Following the completion of all assessments on Day 8 (Visit 5A) for the low-dose cohort (cohort 1) sentinel subject pair, the DEC will review the experience of these subjects. If the safety and tolerability of study drug in both sentinel subjects is acceptable in the opinion of the DEC, and none of the stopping criteria are met, a recommendation to progress to the expansion cohort at a given dose level will be made to the Sponsor by the DEC, and all remaining subjects in cohort 1 may commence dosing.

#### **6.4.2. Dose Escalation Cohorts**

##### *Cohort 1*

Once data at the Day 8 time point for the sentinel subjects are reviewed and judged satisfactory by the DEC, all remaining (3) subjects in this cohort can initiate dosing as described previously.

Following completion of all assessments on Day 8 (Visit 5A) for the entirety of cohort 1, the DEC will review safety and tolerability data. Once all applicable data through the Day 8 time point are reviewed and judged satisfactory by the DEC, a recommendation will be made to the Sponsor and documented regarding dose progression/escalation.

##### *Cohorts 2 Onward*

Following DEC evaluation and approval of the safety of the previous dose level, the next higher dose level may initiate dosing for four subjects, who will be clinically evaluated at 48 hours, 72 hours and 7 days post-dose initiation (Day 8). Following completion of the 1-week clinical assessment comprising 7 days of continuous dosing, the DEC will review the safety and tolerability data. Once all applicable data at the 1-week point are reviewed and judged

satisfactory by the DEC, a recommendation to the Sponsor will be made and documented regarding dose progression.

Alternatively, safety data from the previous cohort may result in a DEC recommendation to repeat the previous dose level in the next sequential numbered cohort for an additional four subjects. These additional subjects will be clinically evaluated at 48 hours, 72 hours and 7 days post-dose initiation (Day 8). If the DEC judge the additional safety and tolerability data at that dose level to be satisfactory, a recommendation will be made and documented regarding dose progression and the next higher dose level can initiate dosing in the next sequential numbered cohort.

As there are three dose levels (low-, mid- and high-dose) with this adaptive design there can be as many as six dose escalation cohorts following the sentinel pair (should there be two cohorts at each dose level due to safety and tolerability findings at each DEC meeting).

#### **6.4.3. Dose Expansion Cohort**

The highest well-tolerated dose of EXN407 (as determined by the DEC – see [Section 8.4](#)) will be evaluated in a subject expansion cohort consisting of up to a maximum of 40 subjects (randomized to receive EXN407 at the selected dose or vehicle, in a 2:1 ratio). Subjects will receive treatment for 84 days, with 28 days of post-treatment follow-up and an EOS Visit. The DEC will meet to discuss safety and tolerability at intervals to be defined in the DEC charter.

#### **6.4.4. Rationale for Starting Dose**

Dosing EXN407 BID at 1.5 mg/mL (30  $\mu$ L per dose) via topical instillation is predicted to be safe for human eyes, and the selected concentration is supported by *in vivo* animal studies as being effective and safe. EXN407 GLP NHP toxicology study (13-week dosing, followed by 4-week recovery period), as well as a pharmacological activity mouse and NHP study, were performed to identify appropriate doses for human treatment. In the mouse model of laser-induced choroidal neovascularization, EXN407 66 ng/mL (10  $\mu$ L, BID) eye drops significantly reduced vessel growth quantified by area and intensity of new vasculature after 7 days compared to vehicle-control (Study 143833). In the monkey pharmacodynamics (PD) studies, intraocular treatment with 1.5 mg/mL of EXN407 (35  $\mu$ L, BID) significantly reduced retinal pSRSF1 and total VEGF-Axxxa compared to control. Further, no adverse effects were observed at 1.5 mg/mL (35  $\mu$ L) of clinical formulation of EXN407 administered to healthy NHP eyes four times daily, for 13 weeks. Similar, 10-day tolerability study in rabbits showed that, after multiple daily instillations of 50  $\mu$ L of EXN407 up to 1.5 mg/mL over 10 days, no body weight changes and no particular ocular clinical observations (Draize, McDonald Shadduck, electroretinogram [ERG], Intraocular pressure [IOP] or Corneal sensitivity) or macroscopic and microscopic findings were observed compared to control.

Overall, based on the GLP 13-week repeat dose ocular topical toxicity study in monkeys, the NOEL was considered to be the highest dose of 0.0525 mg/eye/dose or 0.21 mg/eye/day (QID). The proposed FIH dose is 0.015 mg/eye/dose (BID) or 0.030 mg/eye/day and the highest proposed human dose is 0.045 mg/eye/dose (BID) or 0.090 mg/eye/day. Thus, the FIH dose for a single eye drop and BID dosing is 14-fold and 7-fold lower than the no observed effect level (NOEL) in the monkey 13-week study. The top proposed human dose for a single eye drop and BID dosing is 4.7-fold and 2.3-fold lower than the NOEL dose in the monkey study.

In terms of systemic exposure, at the top human dose of 0.045 mg/eye/dose (BID) or 0.090 mg/eye/day, the  $C_{max}$  would not exceed 2.3 nM as supported by the  $C_{max}$  obtained in the 10-day repeat dose rabbit study and 13-week GLP repeat dose monkey study at the highest 1.5 mg/mL dose.

## **6.5. Subject Population**

The study will be conducted in male and female subjects with diabetes mellitus (Type 1 or Type 2) and center involved DME in the study eye, aged  $\geq 18$  years (inclusive) at the time of informed consent.

Women of childbearing potential (WOCBP) will be included and are subject to contraceptive requirements during the study from Screening until study completion, including the follow-up period, and for at least 90 days after the last dose of study drug. WOCBP must demonstrate negative pregnancy testing at Screening and before administration of study drug. This is in line with regulatory Guidance on Nonclinical Safety Studies for the Conduct of Human Clinical Trials and Marketing Authorization for Pharmaceuticals (FDA 2010).

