**Diagnosis and Main Criteria for Inclusion:****Inclusion Criteria**

Subjects eligible for enrolment in the study must meet all of the following criteria at Screening and enrolment.

1. Subject is at least 18 years of age inclusive, at the time of signing the informed consent
2. BCVA better than or equal to a 69 ETDRS score (an approximate Snellen equivalent of 20/40 or 6/12) in the study eye using the ETDRS visual acuity scale at Screening or BCVA less than 69 ETDRS score (an approximate Snellen equivalent of 20/50 or 6/15) but who, in the Investigator's opinion, is unsuitable for treatment with anti-VEGF by intravitreal injection or refuses it. Subjects should have no more than a 7-letter difference in BCVA at Screening and baseline Visit.
3. A female subject is eligible to participate if she agrees to use highly effective contraceptive measures (if heterosexually active and a woman of childbearing potential [WOCBP]) from Screening until study completion, including the follow-up period. Acceptable methods of contraception include the use of condoms AND the use of an effective contraceptive that includes:
  - a. Oral contraceptives (The Pill),
  - b. Long-acting implantable hormones,
  - c. Injectable hormones,
  - d. A vaginal ring or an intrauterine device (IUD).Rhythm methods are not considered as highly effective methods of birth control.
4. A female subject must also not be breast feeding and must have a negative pregnancy test prior to start of dosing if of childbearing potential, or must have evidence of non-childbearing potential by fulfilling one of the following criteria at Screening:
  - a. Is postmenopausal defined as aged more than 50 years and amenorrheic for at least 12 months following cessation of all exogenous hormonal treatments.
  - b. Can provide documentation of irreversible surgical sterilization by hysterectomy, bilateral oophorectomy or bilateral salpingectomy but not tubal ligation.
  - c. Is amenorrheic for 12 months and serum follicle-stimulating hormone levels in the postmenopausal range for the institution.
5. Sexually active male subjects where the sexual partner is a WOCBP must be willing to use barrier contraception i.e., condoms, and another acceptable form of contraception (see Inclusion Criteria 3 for acceptable forms) during the study and for 3 months after the last dose of study medication.

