**Duration of Treatment:**

*Screening and Run-in period:* 3-28 days

*Treatment period:*

- 7 days for dose escalation cohorts (numbered cohorts 1, 2, 3, etc.)
- 3 months for dose expansion cohort (84 days ± up to 7 days for Visit windows)

*Follow-up period:*

- 28 days for dose escalation cohorts (± 2 days)
- 28 days for dose expansion cohort (± 7 days)

The overall study duration for an individual subject in the dose escalation cohorts will be approximately 64 days and up to 66 days with the follow-up Visit window.

The overall study duration for an individual subject in the dose expansion cohort will be approximately 5 months (141 days) and up to 5.5 months (156 days) with visit windows.

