### **9.1. Subject Inclusion Criteria**

Subjects eligible for enrolment in the study must meet all of the following criteria at Screening and enrolment.

1. Subject is at least 18 years of age inclusive, at the time of signing the informed consent
2. BCVA better than or equal to a 69 ETDRS score (an approximate Snellen equivalent of 20/40 or 6/12) in the study eye using the ETDRS visual acuity scale at Screening or BCVA less than a 69 ETDRS score (an approximate Snellen equivalent of 20/50 or 6/15) but who, in the Investigator's opinion, is unsuitable for treatment with anti-VEGF by intravitreal injection or refuses it. Subjects should have no more than a 7-letter difference in BCVA at Screening and baseline visit.
3. A female subject is eligible to participate if she agrees to use highly effective contraceptive measures (if heterosexually active and a WOCBP) from Screening until study completion, including the follow-up period. Acceptable methods of contraception include the use of condoms AND the use of an effective contraceptive that includes:
  - a. Oral contraceptives (The Pill),
  - b. Long-acting implantable hormones,
  - c. Injectable hormones,
  - d. A vaginal ring or an IUD.Rhythm methods are not considered as highly effective methods of birth control.
4. A female subject must also not be breast feeding and must have a negative pregnancy test prior to start of dosing if of childbearing potential, or must have evidence of non-childbearing potential by fulfilling one of the following criteria at Screening:
  - e. Is postmenopausal defined as aged more than 50 years and amenorrheic for at least 12 months following cessation of all exogenous hormonal treatments.
  - f. Can provide documentation of irreversible surgical sterilization by hysterectomy, bilateral oophorectomy or bilateral salpingectomy but not tubal ligation.
  - g. Is amenorrheic for 12 months and serum follicle-stimulating hormone levels in the postmenopausal range for the institution.
5. Sexually active male subjects where the sexual partner is a WOCBP must be willing to use barrier contraception i.e., condoms, and another acceptable form of contraception (see Inclusion Criteria 3 for acceptable forms) during the study and for 3 months after the last dose of study medication.

6. Diabetes mellitus (Type 1 or Type 2). Any of the following will be considered to be sufficient evidence that diabetes is present:
  - a. Current regular use of insulin for the treatment of diabetes

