### **12.3.5. Visit 6A – EOS / Day 36 ( $\pm 2$ Days)**

Subjects will return to the clinic for their EOS visit on Day 36 with a window of  $\pm 2$  days.

The following procedures will be conducted:

- Concomitant Medications
- AEs since the last visit
- Vital Sign Measurements - systolic and diastolic BP, heart rate, respiratory rate, body temperature
- Physical Exam (targeted physical exam only, see [Section 14.1.4](#))
- Weight measurement
- BCVA – to be done prior to all procedures requiring pupil dilation
- Blood draw for hematology, serum chemistry and coagulation
- Single 12-lead ECG
- Collection of urine for urinalysis
- All remaining Ophthalmic Exams/ Ophthalmoscopy
- SD-OCT
- CFP
- Tonometry to measure IOP
- Corneal pachymetry

This visit marks the end of participation in this study.

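### Inclusion criterion 3 and Section 9.4.3 omit the 90-day post-dose contraception period that Section 6.5 requires for women of childbearing potential, leaving them about two months short

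*Combined protocol and SAP*

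**What the plan says.** Four places in the protocol set the contraception period for women of childbearing potential.

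- **Section 6.5 (Subject Population):** from Screening to study completion with follow-up, "and for at least 90 days after the last dose of study drug".
- **Synopsis, inclusion criterion 3:** "from Screening until study completion, including the follow-up period". No post-dose period is given.
- **Section 9.1, inclusion criterion 3:** the same period as the synopsis.
- **Section 9.4.3 (Contraception), paragraph on women:** the same period again.

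For men whose partners are of childbearing potential, inclusion criterion 5 and Section 9.4.3 do state a post-dose period: "during the study and for 3 months after the last dose of study medication".

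The synopsis (Duration of Treatment) sets follow-up at 28 days, with a window of ±2 days in escalation and ±7 days in expansion. Section 9.3 counts the 28 days from the last dose. Section 12.3.5 says of the escalation end-of-study visit: "This visit marks the end of participation in this study".

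**The concern.** Section 6.5 is background text. Criterion 3 is what a woman must agree to in order to enrol, and Section 9.4.3 is where a site would look for the contraception rule. Section 9 allows no deviation from the eligibility criteria as written. A site working correctly from those sections would obtain a shorter commitment than the protocol requires elsewhere.

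The rule for men makes the omission easier to misread. A reader who finds a post-dose period for men and none for women could conclude that none applies to women, although the women are the ones dosed. The protocol gives no reason for a shorter period in women, and Section 6.5 points the other way.

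At stake is a participant-safety requirement in a first-in-human study. Table 5 schedules urine pregnancy tests only at Screening and Day 1, so after the first dose the contraception commitment is the main scheduled protection.

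**Working it through.** **Inputs**

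| Quantity | Value | Source |
|---|---|---|
| Required period after last dose, women | at least 90 days | Section 6.5 |
| Follow-up, escalation | 28 ± 2 days | Synopsis, Duration of Treatment |
| Follow-up, expansion | 28 ± 7 days | Synopsis, Duration of Treatment |
| Last dosing day / end-of-study visit, escalation | Day 7 / Day 36 ± 2 | Sections 6.4.1 and 12.3.5 |
| Last dosing day / end-of-study visit, expansion | Day 84 / Day 113 ± 7 | Sections 12.4.1.2 and 12.4.8 |

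The protocol states no shortfall, so there is no figure of its own to reproduce. The formula is: shortfall = 90 − (days from last dose to study completion), with study completion read as the subject's end-of-study visit.

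**Using the stated follow-up length**

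- Nominal, both parts: 90 − 28 = 62 days.
- Escalation window: 90 − 30 = 60 to 90 − 26 = 64 days.
- Expansion window: 90 − 35 = 55 to 90 − 21 = 69 days.

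**Using scheduled study days**

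- Escalation: the 90 days end on Day 7 + 90 = Day 97. Shortfall 97 − 36 = 61 days; window 97 − 38 = 59 to 97 − 34 = 63.
- Expansion: the 90 days end on Day 84 + 90 = Day 174. Shortfall 174 − 113 = 61 days; window 174 − 120 = 54 to 174 − 106 = 68.

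The two counts differ by one day because the scheduled visit falls 29 days after the last dosing day (36 − 7 and 113 − 84). The difference does not affect the conclusion.

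**Does other text close the gap?** The follow-up mentioned in criterion 3 is the 28-day period, so it cannot supply the 90 days. Section 12.5 places the early-termination visit 28 days after the last dose, which leaves the same gap. Outside Section 6.5, no visible section extends contraception for women beyond study completion.

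**The case against.** The mismatch itself is not in dispute. The case against giving it weight has four parts.

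1. **The size depends on an undefined term.** The sentence ending participation at the end-of-study visit is in the escalation section; Section 12.4.8, for expansion, has none. Other sections use completion of the study for the whole trial (Sections 11.7 and 21.2). This stands as a caveat. The per-subject reading is the more natural one beside a reference to follow-up. On the trial-wide reading, women dosed early would be covered, but any woman whose last dose falls within 90 days of trial end would still be short.

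2. **The ranges assume dosing is completed.** Sections 8.1 and 8.5 keep subjects who stop study drug in the scheduled assessments. An expansion subject followed to Day 113 would have no shortfall if her last dose were on or before Day 23 (113 − 23 = 90). This is a fair limit on the ranges. However, the synopsis and Section 8.1 also place the end-of-study visit for these subjects 28 days after the last dose, and on that schedule the nominal 62 days returns.

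3. **The intended period is not proven.** Three statements omit the 90 days and one includes it, and the guidance that Section 6.5 cites is not available here. Choosing the longer period is therefore a prudent default. It does follow a requirement the sponsor has written down, and it is about the same as the 3 months set for men.

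4. **The practical harm may be small.** Section 6.3 expects very low systemic absorption, the number of women affected is not given, and the consent form may already state 90 days. This lowers the likely consequence. It does not bring the operative criteria into line with Section 6.5.

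**Conclusion.** The concern holds. Criterion 3 and Section 9.4.3 ask women of childbearing potential for about two months less contraception after the last dose than Section 6.5 requires: nominally 62 days, and 54 to 69 days across visit windows and day-counting conventions. These figures assume that study completion means the subject's own end-of-study visit and that this visit takes place about 28 days after her last dose.

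Because following Section 6.5 meets every section, this is an omission and not a contradiction. It should be corrected, since a site that follows the eligibility criteria to the letter would under-apply the protocol's own safety requirement. No endpoint, analysis or sample-size figure is affected, and nothing is concluded about what participants are actually told.

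**What to change.** Add "and for at least 90 days after the last dose of study drug" to inclusion criterion 3 in the synopsis and in Section 9.1, and to the paragraph on women in Section 9.4.3. Check that the consent form gives the same period. If the sponsor considers the 28-day follow-up sufficient, it should instead amend Section 6.5 and give the reason; the two durations should not both remain.

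The cost is one clause in three places and a check of the consent form. The downside is a longer contraception commitment for the women affected.
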